7.2 VOLUNTEER DISCONTINUATION/WITHDRAWAL FROM THE STUDY

Participants are free to withdraw from participation in the trial at any time upon request.

An Investigator may discontinue or withdraw a participant from the trial for the following reasons:

- Pregnancy
- Significant trial intervention non-compliance
- If any clinical AE, laboratory abnormality, or other medical condition or situation occurs (or an exclusion criteria is revealed that was not previously recognised) such that continued participation in the trial would not be in the best interest of the participant

The reason for participant discontinuation or withdrawal from the trial will be recorded on the eCRF. Participants who sign the informed consent form and are randomised but do not receive malaria inoculation may be replaced. Participants who sign the informed consent form, and are randomised and receive malaria inoculation, and subsequently withdraw, or are withdrawn or discontinued from the trial, may be replaced after mutual agreement between the Sponsor and the PI. The decision regarding the replacement of participants will be documented.

Participants who have been inoculated and indicate they wish to withdraw from the trial must complete the full course of definitive antimalarial treatment.

Participants will be reminded of the importance of completing their antimalarial treatment. Additionally, the PI will demonstrate due diligence in following up with the participant to ensure antimalarial therapy has been completed successfully. Participants may also be treated with Primacin™ if gametocytaemia is suspected from parasite lifecycle qRT-PCR or by the presence of stable low-level parasitaemia to ensure complete clearance of gametocytes. The decision to administer Primacin™ will be made by the PI in consultation with the medical monitor.

If a participant is withdrawn from the trial, the Sponsor will be informed immediately. If there is a medical reason for withdrawal, the participant will remain under the supervision of the PI until satisfactory health has returned, or medical/clinical care has been transferred to the participant's general practitioner or to a hospital consultant.

The PI will make every effort to determine the primary reason for a participant's withdrawal from the trial and record this information in the eCRF. If the participant is withdrawn from the trial procedures or follow-up for any reason, with the participant's permission, medical care will be provided for any SAEs that occurred during participation in the trial until the symptoms of any SAEs are resolved and the participant's condition becomes stable.

7.3 LOST TO FOLLOW-UP

If a participant does not attend a scheduled visit, the Investigator will apply due diligence by documenting all steps taken to contact the participant (e.g., dates of phone calls, registered letter, home visit, etc.) in the source documents.

It will be explained to the participants during the consenting process and throughout the trial that they must be readily contactable. The period from inoculation to definitive antimalarial treatment is the critical period for participant safety because they may have blood stage parasites. A participant will be deemed "missing" if they fail to reply to communication to their personal mobile phone and nominated contact's number after 24 h. If after 36 h the participant fails to respond then an Investigator will organise a home visit. Subsequently, if the participant is still absent, an Investigator will request assistance from the local police to locate the missing participant. Once the participant is found, the participant will be administered Riamet if this has not already been administered^{*}, and Primacin[®] if required.

A participant will be deemed lost to follow-up in the unlikely event that the participant is unable to be contacted or located despite all of the above measures. This is not anticipated to occur prior to administration of antimalarial rescue treatment, as in this situation, all efforts to locate the participant, including with assistance from local police, would continue until the participant is located and treated.

8 STUDY ASSESSMENTS AND PROCEDURES

8.1 STUDY CONDUCT SCHEDULE

8.1.1 SCREENING VISIT (DAY -28 TO DAY -1)

A screening visit will be scheduled after an initial phone interview conducted by clinical trial unit staff has occurred to review background information. For the screening visit, potential participants will be asked to come to the clinical trial unit after an overnight fast of ≥8 hours. During this initial screening visit, an Investigator will discuss the details of the trial with the potential participant, and the participant will read the Participant Information Sheet and be encouraged to ask questions. The potential participant will be fully informed of the nature of the trial at this time. Individuals willing to be considered for inclusion may

sign the Informed Consent Form during the screening visit or may return to the clinical trial unit after further consideration of the trial and the Informed Consent Form. The participant will be given a copy of the Participant Information Sheet and signed Informed Consent Form for their records. The consenting process will be documented in the source notes.

The signed and dated originals will be held on file by the clinical trial unit. Participation consent must be obtained from all individuals prior to screening tests. Once the potential participant has provided written consent to participate, the pre-trial screening may be initiated.

Participants who complete all screening procedures and satisfy all entry criteria will be considered eligible to participate in this trial. For eligibility parameters, unscheduled visits may be planned to assess, confirm, and follow-up on out-of-range clinical laboratory test, vital sign, or ECG values that determine a participant's eligibility. In case of doubt, the PI is to confer with the Medical Monitor for agreement.

If screening laboratory results are abnormal (e.g. HIV testing), the participant will be referred for appropriate counselling. If any clinically significant abnormalities are detected during screening, the participant will be referred to a general practitioner or medical specialist for follow-up tests as appropriate.

Participants will be advised of the requirement to repeat some screening tests during the Day -3 to Day -1 eligibility confirmation visit (unless screening occurs within eligibility Day -3 to -1 window) and/or on inoculation day to determine their continuing eligibility.

The screening will be conducted within 28 days prior to the inoculation day and will include all activities listed below:

- A screening number will be assigned to each participant (as per clinical trial unit standard format).
- Elicit a complete medical history and use of medications.
- Elicit a social history including recreational drug, alcohol and tobacco use.
- Elicit demographic data.
- Record body height and weight.
- Perform alcohol breath test.
- Perform urine drug screen.
- Perform complete physical examination.
- Ask participant to complete the Beck Depression Inventory.
- Assess the cardiovascular disease risk (as per the Australian Absolute Cardiovascular Disease Risk Calculator).
- Record vital signs (supine and standing blood pressure and heart rate).
- Obtain a 12-lead ECG.
- Collect urine for urinalysis.
- Collect NPA for SARS-CoV-2 testing (if screening visit is conducted two days prior to inoculation).
- Collect blood samples for haematology and biochemistry (including lipids for cardiovascular risk factor), red cell antibodies, quantitative G6PD, serology and coagulation profile.
- Perform serum β -hCG pregnancy test for all females, and FSH test for post-menopausal females.

- Verify participant meets inclusion/exclusion criteria.

8.1.2 ELIGIBILITY CONFIRMATION VISIT (DAY -3 TO DAY -1)

The participants (including reserve participants) will report to the clinical trial unit between Day -3 to Day -1 for the following baseline assessments, unless screening laboratory assessments were conducted within this period, in which case repeat sampling will not be required.

This visit will include:

- Collect blood samples for haematology and biochemistry.
- Collect urine for urinalysis.
- Collect NPA for SARS-CoV-2 testing.

The timing of these assessments is to ensure that results are available for review by the Investigator prior to inoculation on Day 0.

8.1.3 MALARIA CHALLENGE AGENT ADMINISTRATION (DAY 0)

Participants, including up to three reserve participants per inoculation day, will report to the clinical trial unit on the morning of the day of inoculation. The Investigator will review the participants' screening and eligibility confirmation visit results prior to their inoculation.

On admission to the clinical trial unit, participants will be required to undertake further procedures to determine whether they remain eligible to be enrolled. A reserve participant may be asked to replace a participant who does not continue to meet eligibility. The reserve participants will be compensated for the study visit even if not inoculated, as described in the Participant Information Sheet and Consent Form.

The procedures that will be undertaken prior to inoculation include:

- Verify that all applicable eligibility criteria have been met.
- Elicit information regarding any new medical conditions, illnesses and medication use since screening visit.
- Perform RAT for SARS-CoV-2 testing
- Perform alcohol breath test.
- Perform urine drug screen.
- Perform urine β -hCG pregnancy test for WOCBP.
- Perform abbreviated physical examination.
- Record vital signs
- Obtain a 12-lead ECG.
- Cannulate participants with an indwelling intravenous cannula (20 or 22 gauge) for the malaria parasite challenge agent, and record which arm is utilised.
- Collect blood samples for;
 - malaria 18S qPCR (baseline sample),
 - safety serum retention sample,

- malaria future research sample (if participant has consented)

Administration of the malaria challenge agent:

- Administer the malaria challenge agent of ~2,800 viable *P. falciparum* 3D7 infected human erythrocytes intravenously.
- Observe for a minimum of 60 minutes after inoculation to evaluate for immediate adverse reactions.
- Educate participants on signs and symptoms of malaria.
 - a. Signs of malaria include fever (oral temperature above 38°C), chills/shivering/rigors, tachycardia, hypotension
 - b. Symptoms of malaria include headache, myalgia, arthralgia, fatigue/lethargy, malaise, sweating/hot spells, loss of appetite, nausea, vomiting and abdominal discomfort.
- Provide participants with diary cards and thermometers to record any temperature readings during the study in the event of symptoms of fever. Participants will also record symptoms, details of self-administered take home antimalarial rescue medication and concomitant medications on the diary cards during the study.
- Record AEs and concomitant medications.
- Record vital signs prior to leaving the clinical trial unit (approximately 60 minutes after inoculation).

8.1.4 OUTPATIENT MONITORING PRE-IMP ADMINISTRATION (DAY 1 TO DAY 7)

Monitoring via phone (Days 1 to 3):

During this period, the participants are expected to be asymptomatic. A daily phone call or text message will be made to the participant by clinical trial unit staff to monitor participant well-being and to solicit any AEs and concomitant medications.

Daily visits to the clinical trial unit for monitoring (Days 4 to 7):

Follow-up from Day 4 to Day 7 will be undertaken through daily morning visits to the clinical trial unit.

The following procedures will occur during these visits:

- Perform symptom-directed physical examination if clinically indicated.
- Record vital signs.
- Collect blood sample for malaria 18S qPCR.
- Collect NPA for SARS-CoV-2 testing (Day 6 am)
- Collect blood samples for haematology and biochemistry (Day 7 am)
- Record AEs and use of concomitant medications.
- Check participant diary cards.

8.1.5 INPATIENT OBSERVATION AND IMP ADMINISTRATION (DAY 8 TO DAY 12)

Participants will be admitted to the clinical trial unit for single-dose administration of pyronaridine on Day 8 when parasitaemia for the majority of participants is expected to be above 5,000 parasites/mL.

The following procedures will occur at admission to the clinical trial unit (before pyronaridine administration):

- Perform RAT for SARS-CoV-2 testing
- Perform abbreviated physical examination.
- Obtain and review a 12-lead ECG.
- Record vital signs.
- Perform and review urine β -hCG pregnancy test for WOCBP.
- Record AEs and use of concomitant medications.
- Perform and review alcohol breath test and urine drug screen.
- Review haematology and biochemistry results from Day 7 am collection.
- Cannulate participants with an indwelling intravenous (18 or 20 gauge) cannula.
- Collect blood samples for
 - haematology and biochemistry,
 - malaria 18S qPCR,
 - parasite viability *ex vivo* growth,
 - drug concentration (baseline sample),
 - malaria future research sample (if participant consented)

The following procedures will occur after pyronaridine administration:

- Administer the relevant pyronaridine dose under direct observation.
- Follow up participants as in-patients for up to 96 hours to ensure tolerance of pyronaridine and adequate clinical response.
- Perform symptom-directed physical examination if clinically indicated.
- Record vital signs three times a day (approximately 6 – 8 hours apart) whilst confined.
- Obtain 12-lead ECG once daily while confined.
- Collect blood for haematology and biochemistry at 72 hours post-pyronaridine administration.
- Collect blood for malaria 18S qPCR following pyronaridine administration at 4, 8, 12, 16, 20, 24, 30, 36, 42, 48, 60, 72, 84 and 96 hours (see section 8.4 for time allowed time windows).
- Collect blood samples for drug concentration at 1, 2, 3, 4, 6, 8, 12, 16, 20, 24, 30, 36, 42, 48, 60, 72, 84 and 96 hours (see section 8.4 for time allowed time windows).
- Collect blood for parasite viability *ex vivo* growth at 4, 8, 12, 16, 20, 24, 48, 72 and 96 hours (see section 8.4 for time allowed time windows).
- Record AEs and use of concomitant medications.

Participants will be confined in the clinical unit for up to 96 hours to ensure tolerance of pyronaridine and adequate clinical response. In the event that parasitaemia is not reduced from peak parasitaemia value by approximately 10-fold during the confinement period, and/or parasite regrowth occurs (≥ 5000 parasites/mL and a 2-fold parasitaemia increase within 48 hours), rescue treatment with Riamet® will be initiated.

If participants are clinically well at the end of the 96 hour confinement, they will be discharged and monitored on an outpatient basis up to the EOS visit. Before exit from confinement, clinical trial unit

nursing staff must confirm with the Investigator if any participant requires symptom-directed physical examination prior to discharge.

The following procedures will occur prior to discharge from the clinical trial unit (96 hours):

- Perform symptom-directed physical examination if clinically indicated.
- Obtain a 12-lead ECG.
- Record vital signs.
- Collect blood samples for
 - malaria 18S qPCR,
 - drug concentration,
 - parasite viability *ex vivo* growth
- Record AEs and use of concomitant medications.

8.1.6 OUTPATIENT MONITORING POST-IMP ADMINISTRATION (DAY 13 TO DAY 50±2)

Follow up visits will be undertaken on an out-patient basis for clinical evaluation and blood sampling. Follow up visits will occur at least three times per week (may occur more frequently if clinically indicated) until Riamet® treatment.

The following procedures will take place during these visits:

- Obtain 12-lead ECG.
- Record vital signs.
- Record AEs and use of concomitant medications.
- Check participant diary cards.
- Perform symptom-directed physical examination if clinically indicated.
- Collect blood samples for drug concentration at 120 (Day 13±1), 168 (Day 15±1), 216 (Day 17±1), 288 (Day 20±1), 336 (Day 22±1), 384 (Day 24±1), 456 (Day 27±1), 504 (Day 29±1), 576 (Day 32±2), 744 (Day 39±2) and 864 (Day 44±2) hours (Days) post-dose
- Collect blood samples for malaria 18S qPCR at least 3 times per week until Riamet® treatment, timing will be at PI discretion based on previous 18S qPCR results and clinical symptoms. Where possible 18S qPCR blood sampling should coincide with drug concentration sampling time-points to avoid bringing participants back for outpatient visits unnecessarily.
- Collect blood samples for haematology and biochemistry on Days 15±1, 22±1, 29±1, 37±2 and 44±2.
- Collect blood samples for parasite lifecycle stage qRT-PCR at Investigator's discretion (if gametocytæmia is suspected based on low and stable parasitaemia). These samples should be aligned with the 18S qPCR to avoid bringing participants back for outpatient visits unnecessarily.
- Collect blood samples for malaria future research (if participant has consented) on Days 15±1 and 29±1.

8.1.7 ANTIMALARIAL RESCUE TREATMENTS

All participants will receive compulsory antimalarial rescue treatment with Riamet® on Day 47±2, or earlier in the following cases:

- Parasitaemia is not reduced by approximately 10-fold at the end of the 96 hour confinement period (Day 12) when compared with peak parasitaemia.
- Parasite regrowth occurs after an initial reduction in parasitaemia, with regrowth defined as ≥ 5000 parasites/mL and a 2-fold parasitaemia increase within 48 hours.
- Volunteer discontinuation/withdrawal from the study (see Section 7.2).
- Investigator's discretion in the interest of participant safety.

As qPCR results are not received in real-time, rescue may occur when these parasitaemia thresholds are presumed to have occurred.

If gametocytes are present as determined by qRT-PCR at any time point after the confinement period, a single dose of Primacin® will be administered at the Investigator's discretion. A participant's G6PD status will determine the dose of primaquine administered. If an allergy or contraindication to Riamet® or Primacin® develops, Malarone® will be administered. In the rare event that a participant cannot tolerate oral drugs, participants will be admitted to hospital and I.V. artesunate will be administered.

The following procedures will be performed prior to antimalarial rescue treatment:

- Perform symptom-directed physical examination if clinically indicated.
- Obtain a 12-lead ECG.
- Record vital signs.
- Record AEs and use of concomitant medications.
- Check participant diary cards.
- Collect blood samples for
 - haematology and biochemistry,
 - malaria 18S qPCR,
 - drug concentration
- Collect sample for parasite viability *ex vivo* growth. **NOTE only if antimalarial rescue treatment is administered prior to Day 47±2.**

Please note if a participant receives antimalarial rescue treatment after administration of pyronaridine but prior to Day 47±2, drug concentration, haematology, biochemistry and future malaria research blood collection will still be required for the full duration of the trial. Following antimalarial rescue treatment blood will be taken for 18S qPCR at the completion of Riamet and until at least one negative result is obtained.

8.1.8 END OF STUDY VISIT (DAY 50±2)

The EOS visit must occur at a minimum 3-days after commencement of compulsory antimalarial treatment.

The following procedures will be performed at the EOS visit:

- Perform a complete physical examination.
- Obtain a 12-lead ECG.
- Record vital signs.
- Record body weight.
- Record AEs and use of concomitant medications.
- Collect urine for urinalysis.
- Collect blood samples for
 - haematology and biochemistry,
 - serum β -hCG pregnancy test for WOCBP,
 - RBC alloantibodies,
 - serology,
 - malaria 18S qPCR,
 - drug concentration,
 - safety serum retention sample,
 - malaria future research sample (if participant consented)
- Collect diary card.

If a participant is unwell with detectable parasitaemia or at the Investigator's discretion, the participant may be asked to return to the clinical trial unit after the EOS visit for safety follow up.

8.2 PHARMACOKINETIC AND PHARMACODYNAMIC ASSESSMENTS

8.2.1 PHARMACOKINETICS

Blood will be collected to quantify whole blood pyronaridine concentrations for PK analysis. PK data will be used to calculate the PK/PD parameters of pyronaridine using a population PK model (the primary endpoint). PK parameters of pyronaridine will also be calculated using non-compartmental methods (secondary endpoint).

Samples will be analysed for pyronaridine blood concentrations using a validated analytical method in compliance with the SOPs of the laboratory performing the analyses. Assays will be performed in a Sponsor approved laboratory.

Blood for pyronaridine concentrations will be collected pre-pyronaridine administration on Day 8, then at the following hours post-pyronaridine administration while confined in the clinical unit: 1, 2, 3, 4, 6, 8, 12, 16, 20, 24, 30, 36, 42, 48, 60, 72, 84 and 96 hours. As outpatients, participants will have blood collected

on the following days: 13, 15, 17, 20, 22, 24, 27, 29, 32, 39, 44, 47 and 50. Allowed time windows for sample collection are specified in Section 8.4.

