3 OBJECTIVES AND ENDPOINTS

OBJECTIVES	ENDPOINTS
Primary	
To characterise the PK/PD relationship of pyronaridine in healthy participants experimentally infected with blood stage P. falciparum .	The PK/PD relationship between pyronaridine blood concentrations and blood stage asexual parasitaemia.
Secondary	
To evaluate the safety and tolerability of single oral doses of pyronaridine in healthy participants experimentally infected with blood stage P. falciparum .	The safety and tolerability of pyronaridine will be determined by recording the incidence, severity and relationship to pyronaridine of adverse events (as determined by clinical, laboratory and ECG examinations) from Day 8 up to Day 50±2.
To characterise the parasite clearance kinetics following single doses of pyronaridine in healthy participants experimentally infected with blood-stage P. falciparum .	The parasite clearance kinetics following dosing with pyronaridine will be determined by calculating the parasite reduction ratio over a 48 hour period (PRR ₄₈) and corresponding parasite clearance half-life (PCt _{1/2}).
To characterise the pharmacokinetics of pyronaridine following single oral dose administration in healthy participants experimentally infected with blood stage P. falciparum .	The pharmacokinetics of pyronaridine will be determined by calculating the following parameters using non-compartmental methods: C _{max} , T _{max} , t _{lag} , AUC _{0-last} , AUC _{0-∞} , CL/F, Vz/F, λz, t _{1/2} .
To characterise the effect of pyronaridine on P. falciparum 3D7 parasite viability using phenotypic and molecular approaches.	Parasite growth in ex vivo cultures.

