8.4 ALLOWED TIME WINDOWS

The following time windows will be allowed for vital signs recording, ECGs and blood sampling for clinical laboratory evaluations:

Time point	Allowed time window
Malaria inoculation (Day 0)	± 4 hours
Outpatient monitoring pre-IMP (Days 4-7)	± 12 hours
Inpatient observation pre-IMP (Day 8)	± 2 hours
Inpatient observation ≤24 hours post-IMP (Day 8-9)	± 30 minutes
Inpatient observation >24 hours post-IMP until discharge (Day 9-12)	± 60 minutes
Outpatient monitoring from discharge up to and including Day 30	± 24 hours
Outpatient monitoring from Day 31 until EOS visit	± 2 days

The following time windows will be allowed for blood sampling to quantify pyronaridine blood concentrations and to monitor malaria parasitaemia:

Time point	Allowed time window
Malaria inoculation (Day 0)	± 4 hours
Outpatient monitoring pre-IMP (Days 4-7)	± 12 hours
Inpatient observation pre-IMP (Day 8)	± 60 minutes
Inpatient observation ≤24 hours post-IMP (Day 8-9)	± 30 minutes
Inpatient observation >24 hours post-IMP until discharge (Day 9-12)	± 60 minutes
Outpatient monitoring from discharge up to and including Day 30	± 24 hours
Outpatient monitoring from Day 31 until EOS visit	± 2 days

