11.2.2 Imputation of Non-Numerical or Negative Values

The imputation of non-numerical or negative values reported in the input data set will be performed as follows:

- Pre-dose sample times will be entered as zero
- Values that are below the limit of quantification (BLQ) obtained prior to the C_{max} will be entered as zero
- Values that are BLQ after the C_{max} will be treated as missing
- Pharmacokinetically plausible concentration value(s) below LLOQ at time points between two measurable concentration values are replaced by the LLOQ/2 value, flagged and included in the PK evaluation. In the event of an anomalous below LLOQ result mid profile, the data will be interrogated by the pharmacokineticist and raised with the client before being altered.
- Should partial AUCs be required then values that are BLQ after C_{max} may be imputed as zero for these partial areas if lambda-z cannot be determined
- Values that are quantifiable after at least 2 consecutive BLQ values after C_{max} will be treated as missing for the calculation of PK parameters
- Actual time from dose administration will be used for parameter estimation except for the pre-(first) dose data point which will be set to the nominal time of 0 hour. Data with missing time information will be discarded.
- Values that are reported as "No Result" or "No Sample" etc. will be treated as missing

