11.2.3 Rules for Pharmacokinetic Parameter Estimation using WinNonlin

Blood concentration vs time profiles of pyronaridine will be generated for each subject. Pharmacokinetic parameters will be estimated using standard Phoenix WinNonlin methods, details of which may be found in the documentation accompanying the WinNonlin software package. The following constraints will apply:

Parameter Estimation	Constraint
Trapezoidal Method	Linear trapezoidal linear/log interpolation method
Number of Points used for Lambda-z	At least 3, not including C_{max}
Minimum Requirements for AUC	At least 3 consecutive quantifiable concentrations
Dose	As supplied
Sampling Times	Actual sampling times (for final analysis)

Where possible, the elimination rate constant (lambda-z) will be calculated for all subjects. The value of lambda-z will be determined by the slope of the regression line of the natural log transformed concentrations vs time.

The choice of data points for determination of lambda-z will be applied by the Phoenix software as a default method, the pharmacokineticist who may adjust the selection to provide a more appropriate fit and records of this will be documented in the software data.

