11.2.5 PK parameters

The following parameters will be estimated:

CDISC Term	Parameter	Definition	DP or SF	No. of DP/SF
TMAX	T_{max}	Time of maximum observed concentration	DP	2
TLAG	T_{lag}	The delay between time of dosing and the appearance of concentration	DP	2
CMAX	C_{max}	Maximum observed concentration	SF	3
AUCLST	AUC_{last}	Area under the curve from 0 time to the last measurable concentration	SF	3
AUCIFO	AUC_{0-inf}	Area under the curve from 0 time extrapolated to infinity	SF	3
LAMZHL	$t_{1/2}$	Apparent elimination half-life	DP	2
LAMZ	Lambda-z	Slope of the apparent elimination phase	DP	4

CDISC Term	Parameter	Definition	DP or SF	No. of DP/SF
CLFO	CL/F	Total body clearance after extravascular administration	SF	3
VZFO	V _d /F	Apparent volume of distribution based on the terminal phase after extravascular administration	SF	3

DP=decimal places

SF=significant figures

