11.2.6 Presentation of Results

All bioanalytical data will be listed and summarised according to the nominal sampling timepoint.

All pharmacokinetic parameters generated will be listed and summarised. Where pharmacokinetic data fails to meet the defined criteria in Section 11.2.4. (Data Quality) the affected results will be excluded from the descriptive statistics will be flagged as per exclusion reason.

Bioanalytical and PK Parameters Listings

All bioanalytical and pharmacokinetic NCA parameters generated will be listed in individual tables according to the analyte and treatment. The data listings will be generated as defined by the PK Concentration population.

Bioanalytical and Pharmacokinetic Summary Tables

Bioanalytical and PK parameters summary tables will be performed by SSR.

Summary statistics (i.e., mean, median, SD, CV%, minimum, maximum, n, geometric mean, geometric SD and geometric CV%) will be calculated for PK results for each time point, parameter and treatment.

All summary statistics (i.e., mean, median, SD, CV%, minimum, maximum and n) will be presented for all PK parameters for blood by treatment. Also, geometric mean, geometric SD and geometric CV% will be presented for all PK parameters (except T_{max}) by treatment. The T_{max} summary statistics will be provided as n, minimum, median, and maximum only.

All the data summary tables will be generated as defined by the PK Analysis Set. Additional summary tables might be produced if required and requested.

Bioanalytical and Pharmacokinetic Figures

All arithmetical mean blood concentration vs. time curves will be produced by treatment on both linear/linear and \log_{10} /linear scales.

All spaghetti plots of individual blood concentrations against nominal sampling times after dosing for each treatment will be produced on both a linear/linear and \log_{10} /linear scale. Each volunteer's concentration profile will be represented on these plots with a different symbol and a legend will be included on the plots to define the symbols used.

List of summary tables, listings and figures are in Appendix, Table A.

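### SAP 11.2.6 requires geometric statistics for T_lag, a parameter that on the planned sampling times resolves only to about 1 h and can equal zero

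*Protocol*

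**What the plan says.** Protocol section 3 states, for the PK secondary endpoint: "The pharmacokinetics of pyronaridine will be determined by calculating the following parameters using non-compartmental methods". t_lag is in the list that follows, and in the synopsis. SAP 11.2.5 also includes it, defined as "The delay between time of dosing and the appearance of concentration" and shown to two decimal places.

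Protocol 8.2.1 sets the sampling times: a pre-dose sample, then "post-pyronaridine administration while confined in the clinical unit: 1, 2, 3, 4, 6, 8, 12, 16, 20, 24" and onwards. Section 8.4 allows ±30 minutes for PK samples in this period (the row that begins "Inpatient observation ≤24 hours post-IMP (Day 8-9"). SAP 11.2.2 places the pre-dose sample at 0 h and uses actual times for the rest. It also sets this rule: "Values that are below the limit of quantification (BLQ) obtained prior to the C_{max} will be entered as zero".

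Neither document says how T_lag is assigned from these samples. SAP 11.2.3 says only: "Pharmacokinetic parameters will be estimated using standard Phoenix WinNonlin methods".

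For the summaries, SAP 11.2.6 says "geometric mean, geometric SD and geometric CV% will be presented for all PK parameters", with Tmax as the only exception; Tmax gets n, minimum, median and maximum. Protocol 9.4.3 has the same gap: tmax gets median and range, and every other PK variable gets a geometric mean and CV%.

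The parameter lists disagree. T_lag is in the synopsis, protocol section 3 and SAP 11.2.5. It is absent from protocol 9.4.3 and SAP 3.5.2.3.

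**The concern.** Tmax and T_lag are both times read off the sampling schedule, but only Tmax is summarised as such. T_lag is the one that can be exactly zero, and zeros cannot enter a geometric mean, SD or CV% calculated on the log scale.

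If a dose group contains a zero, the programmer must either report the statistics as not calculable or drop the zeros. Dropping them removes the participants with the earliest appearance of drug, so the reported geometric mean overstates the lag for the group. The plan does not say which will happen, and a reader of the table may not be able to tell.

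The unstated convention matters as well. A participant quantifiable at the 1 h sample has T_lag = 0 if it is the last time before the first quantifiable concentration, and about 1 h if it is the first quantifiable time. That gap is as large as the finest delay the schedule can resolve.

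**Working it through.** The documents state no figure for T_lag, and protocol 9.2 gives no formal sample-size calculation, so there is no planned figure to reproduce.

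**1. Resolution.** The nominal times are 0, 1, 2, 3, 4 h. With ±30 minutes, the first post-dose sample falls between 0.5 and 1.5 h and the second between 1.5 and 2.5 h. T_lag is therefore 0 or an actual sampling time, in steps of about 1 h. Two decimals display it to 0.01 × 60 × 60 = 36 seconds.

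**2. What one zero does.** Take a group of two with T_lag values 0 and 1.00 h.
- Geometric mean = exp[(ln 0 + ln 1.00)/2]. Since ln 0 is minus infinity, the result collapses to 0.
- The geometric SD and CV% have no value, because the SD of the logs does not exist.
- If the zero is dropped, n becomes 1, the geometric mean is 1.00 h, and no SD can be formed.
- The median and arithmetic mean are both 0.50 h and remain computable.

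**3. Chance that a group contains a zero.** Under the last-time-before rule, let p be the probability that the 1 h sample is quantifiable. Then P(at least one zero) = 1 − (1 − p)^n. The sizes shown are n = 2 (the planned Cohort 1 dose groups), n = 6 (a full cohort) and n = 18 (the maximum).

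| p | n = 2 | n = 6 | n = 18 |
|---|---|---|---|
| 0.1 | 0.19 | 0.47 | 0.85 |
| 0.5 | 0.75 | 0.98 | 1.00 |
| 0.9 | 0.99 | 1.00 | 1.00 |

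For example, p = 0.5 and n = 2 gives 1 − 0.5² = 0.75.

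**4. What p might be.** The documents do not give the inputs, so two sets of assumptions were simulated, both with sample times uniform within ±30 minutes.
- Set A: log-normal lag with SD 0.3 on the log scale; drug quantifiable as soon as absorption starts. This favours zeros.
- Set B: log-normal lag with log-scale SD 0.4; first-order absorption with median rate 0.1, 0.3 or 1.0 per h (log-scale SD 0.4); LLOQ at 0.001, 0.01, 0.05 or 0.1 of the plateau concentration; elimination ignored.

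| Median true lag (h) | Share of zeros, A | Share of zeros, B (range) |
|---|---|---|
| 0.25 | 0.999 | 0.24 to 1.00 |
| 0.5 | 0.93 | 0.11 to 0.90 |
| 0.75 | 0.71 | not run |
| 1.0 | 0.47 | 0.02 to 0.47 |
| 1.5 | 0.15 | 0.00 to 0.19 |

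Under the first-quantifiable-time rule there are no zeros. For a median true lag of 0.25 h and an LLOQ at or below 0.01 of plateau, the reported median is 1.00 to 1.02 h.

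**The case against.** The strongest reply is that non-compartmental T_lag is read off the sampling times by construction, exactly as Tmax is, and nobody calls Tmax inestimable. That is right. A reader might infer that T_lag cannot be estimated at all, but a lag that outlasts the first sample is detected at 1, 2, 3 or 4 h. Two decimals are a display format, also used for Tmax.

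A reader might also infer that nearly everyone will be reported as 0.00 h whatever the true lag. The documents do not support this. They give no LLOQ, absorption rate, expected 1 h concentration or T_lag rule, and even under the assumptions most favourable to zeros the share is below half once the median lag reaches 1 h.

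The failure is also conditional and partial. It needs the last-time-before convention and at least one zero in the group. SAP 11.2.6 also plans n, mean, median, SD, CV%, minimum and maximum for every parameter, and these remain computable, except the CV% if all values are zero. No between-dose test of T_lag is planned, and all dose groups share one schedule, so no systematic dose artefact follows. SAP 10.6.2 already models oral absorption.

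All of that stands and limits the size of the point. It does not supply the missing convention or the missing exemption, and it does not reconcile the lists.

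**Conclusion.** The point holds as a minor reporting and consistency matter. Three parts rest on the documents alone: T_lag resolves only to about 1 h and cannot measure a shorter delay; Tmax is exempt from geometric statistics and T_lag is not; and the parameter lists conflict.

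The failure of the geometric statistics rests on one assumption, that T_lag is the last sampling time before the first quantifiable concentration. Under that rule one zero per group is enough, and with two per group that is likely at moderate p (0.75 at p = 0.5) but not certain (0.19 at p = 0.1). The true p cannot be derived from the documents. Under the first-quantifiable-time rule the problem does not arise.

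The effect is confined to one descriptive secondary PK parameter. The primary PK/PD endpoint is not affected.

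**What to change.** - **SAP 11.2.6:** exempt T_lag from the geometric statistics, as for Tmax. Report n, minimum, median and maximum, plus n (%) not yet quantifiable at the 1 h sample.
- **SAP 11.2.5:** state the convention, either the last sampling time before the first quantifiable concentration or the first quantifiable time.
- **Parameter lists:** reconcile the synopsis, protocol section 3 and SAP 11.2.5 with protocol 9.4.3 and SAP 3.5.2.3, and apply the Tmax-type summary to T_lag in protocol 9.4.3 as well.
- **If an absorption delay is of interest:** assess a lag-time term in the population PK model under SAP 10.6.2, which neither names nor excludes one.

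The SAP changes cost a few lines of wording and one extra count in a table. No samples or procedures are added. Deleting T_lag is not required and would cost more: it is a listed endpoint parameter, and protocol 10.1.2 treats a change of endpoints as a substantial amendment.
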